Abbreviation or Term	Definition/Explanation
PFS	Progression free survival
PR	PR interval is measured from the beginning of the P wave to the beginning of the QRS complex in the heart's electrical cycle as measured by ECG or partial response
PK	Pharmacokinetic
QRS	QRS interval is the interval between the Q wave and the S wave in the heart's electrical cycle as measured by ECG; represents the time it takes for the depolarization of the ventricles
QT	QT interval is a measure of the time between the start of the Q wave and the end of the T wave in the heart's electrical cycle as measured by ECG
QTc	QT interval corrected for heart rate using accepted methodology
QTcF	QT interval corrected for heart rate using Fridericia's formula
RP2D	Recommended phase 2 dose
RR	Relapsed or Refractory
$t_{1/2}$	Half-life
t_{max}	Time of maximum observed serum concentration
TPI	Toxicity probability interval
TTR	Time to response
WHO	World health organization

1. Introduction

The purpose of this Statistical Analysis Plan (SAP) is to provide details of the statistical analyses that have been outlined within the protocol amendment 4 for Study 20170173 - AMG 397 dated 09 December 2020. The scope of this plan includes the interim analysis, the primary analysis and the final analysis that are planned and will be executed by the Amgen Global Bio-statistical Science department unless otherwise specified.

2. Objectives, Endpoints and Hypotheses

- **Indications:** Relapsed or Refractory (RR) Multiple Myeloma (MM), Non-Hodgkin's Lymphoma (NHL), Myelodysplastic Syndrome (MDS) or Acute Myeloid Leukemia (AML).

2.1 Objectives and Endpoints

Objectives	Endpoints
Primary	
Part 1 QD2 Monotherapy (MM, NHL, AML) – CLOSED TO ENROLLMENT	

 • Evaluate the safety and tolerability of AMG 397 QD2 monotherapy • Estimate the maximum tolerated doses (MTDs) and/or biologically active doses (eg, recommended phase 2 doses [RP2Ds]) of AMG 397 	
 • Incidence of dose-limiting toxicities (DLTs), treatment-emergent adverse events, treatment-related adverse events and clinically-significant changes in vital signs, physical examinations, electrocardiogram (ECGs) and clinical laboratory tests
Part 2A QW Monotherapy (MDS, AML)	

 • Evaluate the safety and tolerability of AMG 397 QW monotherapy in subjects with MDS or AML 	
 • Incidence of DLTs, treatment-emergent adverse events, treatment-related adverse events and clinically-significant changes in vital signs, physical examinations, ECGs, and clinical laboratory tests
Part 2B QW Monotherapy in Japan (AML)	

 • Evaluate the safety and tolerability of AMG 397 QW monotherapy in subjects in Japan with relapsed or refractory AML • Evaluate the PK of AMG 397 when administered as monotherapy (QW) in Japan 	
 • Incidence of DLTs, treatment-related, treatment-emergent adverse events and clinically significant changes in vital signs, physical examinations, ECGs, and clinical laboratory tests • PK parameters for AMG 397 including, but not limited to C_{max}, AUC, CL, and $t_{1/2}$

Part 2C QW Monotherapy (MM)	

 Evaluate the safety and tolerability of AMG 397 QW monotherapy in subjects with MM 	
 Incidence of DLTs, treatment-emergent adverse events, treatment-related adverse events and clinically-significant changes in vital signs, physical examinations, ECGs, and clinical laboratory tests
Part 3 QW Combination Therapy (MDS, AML, MM)	

 Evaluate the safety and tolerability of AMG 397 combination therapy 
 MDS/AML: AMG 397 + azacitidine MM: AMG 397 + dexamethasone 	
 Incidence of DLTs, treatment-emergent adverse events, treatment-related adverse events and clinically-significant changes in vital signs, physical examinations, ECGs, and clinical laboratory tests

 Estimate the maximum tolerated or recommended combination dose (MTCD) and/or recommended phase 2 combination doses (RP2CD) of AMG 397 	
Secondary	
Part 1 QD2 Monotherapy (MM, NHL, AML) – CLOSED TO ENROLLMENT	

 Evaluate the preliminary efficacy of AMG 397 monotherapy 	
 Overall response rate (ORR) using response criteria per the following: 
 International Myeloma Working Group – Uniform Response Criteria (IMWG-URC) for MM subjects Lugano Classification for NHL subjects Revised International Working Group (IWG) for AML subjects Revised IWG for MDS subjects progression-free survival (PFS) overall survival (OS) time to response duration of response (DOR)

 Evaluate the pharmacokinetics (PK) of AMG 397 	
 AMG 397 PK parameters including, but not limited to, maximum observed concentration (C_{max}), time of maximum observed concentration (T_{max}), area under the concentration time curve (AUC), clearance (CL) and half-life ($t_{1/2}$)

Part 2A QW Monotherapy (MDS, AML), Part 2B QW Monotherapy (AML), and Part 2C QW Monotherapy (MM)
	

 Evaluate the preliminary efficacy of AMG 397 monotherapy (For Part 2B: Japan subjects only) 	
 ORR using response criteria per the following: 
 Revised IWG for AML subjects Revised IWG for MDS subjects IMWG-URC for MM subjects PFS OS time to response DOR

 Evaluate the PK of AMG 397 	
 AMG 397 PK parameters including, but not limited to, C_{max}, T_{max}, AUC, CL, and $t_{1/2}$

Part 3 QW Combination Therapy (MDS, AML, MM)
	

 Evaluate the preliminary efficacy of AMG 397 combination therapy 	
 OR based on investigator assessment per: 
 Revised IWG for MDS subjects 2017 European LeukemiaNet (ELN) criteria in AML subjects IMWG-URC for MM subjects PFS OS time to response DOR

 Evaluate the PK of AMG 397 and azacitidine (Parts 3A and 3B) or dexamethasone (Part 3C) when administered in combination 	
 PK parameters for the combination including, but not limited to C_{max}, AUC, CL, and $t_{1/2}$

Exploratory	
Parts 1, 2 and 3	

Explore pharmacokinetic/ pharmacodynamic (PK/PD) relationships for safety and/or efficacy endpoints	
AMG 397 exposure/efficacy and exposure/safety relationships

Demonstrate AMG 397 inactivation of myeloid cell leukemia sequence 1 (MCL1) by the activation of BAX and caspase 3 in circulating monocytes or blast cells, and/or the decrease of circulating monocytes or blast cells	
Expression of BAX and Caspase 3 in monocytes or blast cells, circulating monocyte counts, circulating blast counts

Evaluate the correlation of clinical responses to disease-specific features in tumor cells	
Clinical response measures, biomarkers including but not limited to protein levels of pro-survival family members, FISH/cytogenetic analysis, gene expression profiling, flow cytometric phenotyping, and DNA sequencing

Evaluate changes to immune cell subsets in peripheral blood due to MCL1 inactivation	
Immune cell subset frequencies, absolute counts and MFIs in peripheral blood

Parts 3B and C only: Evaluate additional measures of efficacy via minimal residual disease negative (MRD[-]) status with patient response	
MRD[-] status at the time of complete response (CR)

2.2 Hypotheses and/or Estimations

No formal hypothesis testing will be performed. The point estimates and corresponding 2-sided 95% exact CI will be presented on ORR.

3. Study Overview

3.1 Study Design

This is a first-in-human (FIH), multicenter, non-randomized, open-label, phase 1 study evaluating AMG 397 administered orally in adult subjects with selected RR hematological malignancies.

Part 1 of the study was designed to investigate AMG 397 as monotherapy on a twice weekly dosing schedule (ie, once daily for 2 consecutive days followed by 5 days break at a weekly interval [QD2]) in subjects with MM, NHL, and AML (Figure 1). In July 2019, reports of troponin elevations occurring at the highest dose level investigated of

320 mg/m² resulted in the clinical trial being placed on hold. In 2020, the study was redesigned to investigate low weekly doses of AMG 397 including Part 2 ([Figure 2](#), [Figure 3](#)) and Part 3 ([Figure 2](#)) as follows:

- Parts 2A will enroll subjects with MDS or AML (monotherapy [QW]) for dose escalation and subjects with only MDS for dose expansion
- Parts 2B will enroll subjects with AML in Japan (monotherapy [QW])
- Parts 2C will enroll subjects with 1q21 amp MM (monotherapy [QW])
- Parts 3A will enroll subjects with MDS (AMG 397 + azacitidine) for dose escalation and dose expansion
- Parts 3B will enroll subjects with AML (AMG 397 + azacitidine) for dose escalation and dose expansion
- Parts 3C will enroll subjects with 1q21 amp MM (AMG 397 + dexamethasone) for dose escalation and dose expansion

Study Design and Treatment Schema

Figure 1. Part 1 Study Design and Treatment Schema (CLOSED TO ENROLLMENT)

[figure not shown]

Figure 2. Parts 2A, 2C, and 3 Study Design and Treatment Schema (Dose Escalation and Dose Expansion)

[figure not shown]
[figure not shown]

Figure 3. Part 2B Study Design and Treatment Schema (AML Subjects in Japan)

3.2 Sample Size

Up to 240 subjects will be enrolled in the study. A total of 24 subjects were enrolled during Part 1 dose escalation (12 in both Part 1A and Part 1B). Up to 26 evaluable subjects will be enrolled into Parts 2A and 2C monotherapy dose escalation part and up to 20 evaluable subjects into Part 2A (MDS only) dose expansion. Up to 6 subjects will be enrolled into Part 2B. Up to 78 evaluable subjects will be enrolled into each of the combination therapy dose escalation parts (up to 26 each for Parts 3A, 3B, and 3C) and up to 60 evaluable subjects (up to 20 subjects each for 3A, 3B, and 3C) in dose expansion.

The sample sizes are based on practical considerations and it is consistent with conventional oncology studies with the objective to identify the MTC. With 10 subjects, there is a 40% to 65% probability of observing at least 1 adverse event if the true event rate is 5% to 10%. Exact 95% binomial CI will be provided for ORR. With the 20 subjects in each dose expansion group and a 20% ORR, the 2-sided 95% exact CI would be 6% to 44%.

3.3 Adaptive Design

Part 1

A two-parameter Bayesian Logistic Regression Model (BLRM) is used to guide dose escalation. The maximum tolerated dose (MTD) target Toxicity Probability Interval (TPI) for dose-limiting toxicity (DLT) is (0.20, 0.33] and TPIs of (0.33, 0.60] and (0.60, 1.00] are defined as excessive and unacceptable, respectively. The design seeks to identify a dose most likely to have a DLT rate in the target TPI, but with overdose control that limits

the possibility the dose has an excessive or unacceptable DLT rate (Babb et al, 1998). The overdose control limit is defined as less than a 0.40 probability of an excessive or unacceptable TPI. Based on accumulating safety data, the DLRT may implement an overdose control limit of less than a 0.25 probability of an excessive or unacceptable TPI. The probability of a DLT at dose level d_i is assumed to follow a Bernoulli distribution with probability π_i where the logit of π_i increases linearly with the log of the standardized dose in the following 2-parameter logistic model:

$$\log [\pi_i / (1-\pi_i)] = \text{logit}(\pi_i) = \log[a] + \exp(\log[b]) \log (d_i / d_{ref})$$

Where a and b are random variables and d_{ref} is one of the planned doses selected as the reference dose.

A bi-variate normal prior distribution (Neuenschwander et al, 2008) is used for $\theta = (\log a, \log b)$ where the probability that the true DLT rate is ≤ 0.40 at the lowest planned dose of 80 mg is 0.90 and the probability the true DLT rate is ≤ 0.05 at the reference dose of 640 mg is 0.05. These values are selected such that π_i is 0.05 for the starting dose and 0.25 for the reference dose. Model sensitivity to the prior will also be investigated and in particular the BLRM will be examined using a prior having a lower reference dose (eg, 320 mg).

Part 2 and Part 3

Each dose cohort will initially enroll 2-4 subjects in Parts 2A and 2C and 3-4 subjects in Part 3; and up to 10 subjects at the highest dose level or MTD/MTCD may be enrolled. After reviewing all available safety and tolerability data, dose level decisions will be made by the DLRT using a mTPI model based on all evaluable subjects that have been enrolled at current dose. Dose escalation is considered to be complete if one of the following rules is met:

- **The highest planned dose level is evaluated, MTCD has not been defined and no DLTs occur at any dose level.**
- **An MTD or MTCD is identified.**

At least 6 evaluable subjects need to be treated at the dose level of MTCD.

Guidelines for dose level decisions can be found in [Table 1](#). Please note one exception to the guidelines provided in [Table 1](#), a single grade 3 treatment related troponin elevation will result in dose de-escalation regardless of number of subjects treated at current dose.

Table 1. Guidelines for Dose Level Decisions for Parts 2A and 2C and Part 3

No. of DLT-evaluable ^a subjects treated at current dose	Number of DLTs		
	Escalate	Stay at current dose	De-escalate ^b
1	0	-	1
2	0	-	≥ 1
3	0	1	≥ 2
4	0	1	≥ 2
5	0	1	≥ 2
6	0-1	-	≥ 2
7	0-1	2	≥ 3
8	0-1	2	≥ 3
9	0-1	2	≥ 3
10 ^c	0-1	2-3	≥ 4

DLT = dose-limiting toxicity.

^a See Section 6 for definition of DLT evaluable.

^b De-escalate guideline applies only when current dose level and enrollment is allowed to a lower dose level.

^c The maximum number of evaluable subjects at one dose level is 10.

The MTCD is defined as the highest dose with a probability of DLT lower than or close to a targeted toxicity probability of 0.2.

4. Covariates and Subgroups

There are no planned covariates in this study.

If appropriate the following baseline variables may be used to evaluate efficacy endpoints in subgroup analysis: Age at baseline (< 65, ≥ 65), sex, race, prior lines of anti-cancer therapy (1, 2, >2).

5. Definitions

Age at Enrollment

Subject age at enrollment will be determined using the age in years reported in the clinical database.

Baseline

Unless otherwise specified, baseline will be defined as the last assessment before the first dose of investigational product (AMG 397).

Baseline and Post-Baseline Electrocardiogram (ECG) Values in Triplicate

For the three baseline triplicate ECG, the mean of values in a triplicate should be calculated before taking the mean of the three baseline averages.

For all post-baseline ECG, the mean value for measurements taken at the same assessment will be calculated and used in the analysis.

When an ECG is missing within a triplicate, all available data within that assessment visit will be averaged for that time point.

Bazett-corrected QT Interval (QTcB)

The Bazett correction will be calculated from the investigator reported QT (msec) and RR interval (msec): $QTcB = QT / (RR / 1000)^{1/2}$

Best Overall Response (BOR)

Best overall response for a subject is the best observed post-baseline disease response based on investigator assessment. Response criteria are as follows:

- **IMWG-URC for MM**
- **2017 ELN criteria for AML**
- **Revised IWG for MDS**
- **Lugano Classification for NHL**

Dose Limiting Toxicity (DLT)

Unless otherwise specified, investigators determine whether an adverse event qualifies as a DLT per the definition described in the protocol.

DLT Observation Period

The DLT observation period is defined as, at minimum, 28 days after the initial dose of AMG 397. If lead-in dosing period is initiated, the DLT-observation period is defined as the amount of time for subject(s) for each dose cohort to receive at least 1 week of lead-in dose and 3 weeks of target dose.

Duration of Response (DOR)

Duration of response is calculated for subjects who have achieved response (PR or better). It is defined as time from the first observation indicating a response to the subsequent date of disease progression or death, whichever is earlier.

DOR time in months: (date of disease progression or death - date of the first observation of response +1)/30.4

Subjects without disease progression or death until the analysis data cut-off date will be censored at the last adequate disease assessment date.

Fridericia-corrected QT Interval (QTcF)

The Fridericia correction will be calculated from the investigator reported QT (msec) and RR interval (msec): $QTcF = QT / (RR/1000)^{1/3}$

Investigational Product (IP)

IP is used in reference to AMG 397.

Overall Response Rate (ORR)

ORR is the incidence of either PR or better based on investigator assessment. All subjects that do not meet the criteria for response (PR or better) by the analysis cutoff date will be considered as non-responders.

Progression-free survival (PFS)

PFS time is calculated as time from first dose of IP date to disease progression date or death due to any cause, whichever is earlier.

PFS time in months: (date of disease progression or death - first dose of IP date +1)/30.4

Subjects without disease progression or death until the analysis data cut-off date will be censored at the last adequate disease assessment date. If no post-baseline disease assessment, censoring is at the first dose of IP date.

Overall survival (OS)

OS is defined as the time from first dose of IP date until death due to any cause.

OS time in months: (date of death - first dose of IP date +1)/30.4

Patients without event will be censored at their last date known to be alive.

Study Day

Post study day 1: study day = (date –Study Day 1) + 1

Pre study day 1: study day = (date –Study Day 1)

Study Day 1

Study day 1 is defined as the first day of administration of the investigational product after enrollment. The day prior to Study Day 1 is considered Day -1.

Treatment-Emergent Adverse Event (TEAE)

A treatment-emergent adverse event is any adverse event starting on or after the first dose of investigational product, as determined by "Did event start before first dose of investigational product" equal to "No" or missing on the Events eCRF, and up to and including 30 days after the last dose of investigational product excluding events reported after end of study date.

Time to Response (TTR)

Time to response is defined as the time from the first dose of IP until the first documentation of objective response. Only subjects who have achieved objective response will be evaluated for TTR.

TTR time in months: (date of the first observation of response - first dose of IP date +1)/30.4

6. Analysis Sets

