7.1 Interim Analysis and Early Stopping Guidelines

No formal interim efficacy analysis is planned. Safety data will be reviewed on an ongoing basis. Interim safety analyses will be performed for each dose level of each cohort to support the evaluation of safety by the DLRT. After reviewing all available safety data and reviewing the dose recommendation from mTPI, the DLRT will make all dose level and dosing schedule decisions.

Upon the completion of each cohort or each part, interim analyses can be performed to evaluate safety and efficacy data.

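### SAP 3.3 (Parts 2A, 2C and 3): escalation can be declared complete at a DLT-free highest planned dose with no minimum number of evaluable subjects there, because the six-subject minimum is worded only for the MTCD

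*SAP*

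**What the plan says.** SAP 3.3, under Part 2 and Part 3, gives two alternative completion rules; meeting either one is enough.

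- Rule 1: "The highest planned dose level is evaluated, MTCD has not been defined and no DLTs occur at any dose level".
- Rule 2: "An MTD or MTCD is identified".

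The sentence after them reads "At least 6 evaluable subjects need to be treated at the dose level of MTCD". The target is stated below Table 1: "The MTCD is defined as the highest dose with a probability of DLT lower than or close to a targeted toxicity probability of 0.2".

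On numbers per dose, the section says "Each dose cohort will initially enroll 2-4 subjects in Parts 2A and 2C and 3-4 subjects in Part 3", and that "up to 10 subjects at the highest dose level or MTD/MTCD may be enrolled". Table 1 starts at one evaluable subject and reads zero DLTs in one to five subjects as a signal to escalate. Its ceiling is 10 evaluable subjects per dose level.

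For Part 1, the protocol (Synopsis, 3.1 and 6.2.1.2) has an equivalent completion rule for the highest planned dose, with a minimum of six evaluable subjects attached to it.

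**The concern.** Rule 1 applies only while the MTCD is undefined, so a minimum tied to the MTCD does not reach it. Read literally, that minimum also omits the monotherapy MTD named in rule 2.

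Nothing else in the section fills the gap. Enrolment of up to 10 at the top dose is optional. Table 1 forces no further enrolment when the top dose is DLT-free, because there is no higher level to move to. The cohort sizes count subjects enrolled, while SAP 6.2 makes evaluability depend on dose received or on having a DLT, so the evaluable number could be lower still.

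On the rule 1 path no DLT has been seen anywhere, so the top cohort carries most of the information about that dose. SAP 3.1 records that the trial was put on hold after troponin elevations at the highest dose then investigated. Parts 2A and 3A-3C go on to list expansions of up to 20 subjects each. A floor at the top dose is therefore worth stating, and the sponsor has already used one in Part 1.

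**Working it through.** **The plan's own figures.** SAP 3.2 gives a 40% to 65% chance of at least one event in 10 subjects at true rates of 5% to 10%. Check: 1 - 0.95^10 = 0.401 and 1 - 0.90^10 = 0.651. Both agree. The SAP gives no figure for rule 1 itself.

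**Inputs.** Initial cohort n = 2, 3 or 4 (SAP 3.3); proposed minimum 6 (the number used for the MTCD and in Part 1); target DLT rate 0.20 (SAP 3.3). The rate 0.33 is my choice of a clearly too-toxic dose; it is also the upper end of the Part 1 target interval. All results are conditional on DLT-free lower levels, so they need no assumption about how many levels there are. They assume independent subjects, all evaluable, and no voluntary extra enrolment at the top dose.

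**As written.** Rule 1 is met at the top dose with probability (1 - p)^n.

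**With six required.** The first n must be DLT-free and at most one DLT may occur in the 6 - n added, because Table 1 does not de-escalate for one DLT in six: (1 - p)^n × P(Bin(6 - n, p) ≤ 1).

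| p | n | As written | Second factor | With six |
|---|---|---|---|---|
| 0.33 | 2 | 0.449 | 0.599 | 0.269 |
| 0.33 | 3 | 0.301 | 0.745 | 0.224 |
| 0.33 | 4 | 0.202 | 0.891 | 0.180 |
| 0.20 | 2 | 0.640 | 0.819 | 0.524 |
| 0.20 | 3 | 0.512 | 0.896 | 0.459 |
| 0.20 | 4 | 0.410 | 0.960 | 0.393 |

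Example, p = 0.33 and n = 2: 0.67² = 0.449. P(Bin(4, 0.33) ≤ 1) = 0.67⁴ + 4 × 0.33 × 0.67³ = 0.202 + 0.397 = 0.599. The product is 0.269.

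The falls are about 18, 8 and 2 percentage points at 0.33, and about 12, 5 and 2 points at 0.20.

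**Precision.** The one-sided 95% upper bound after zero DLTs in n subjects is 1 - 0.05^(1/n): 78%, 63% and 53% for n = 2, 3 and 4, against 39% for n = 6. This uses the top cohort alone.

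**Room under the caps.** The stated total sums only if 26 is read as per part for 2A and 2C: 24 + 2 × 26 + 20 + 6 + 78 + 60 = 240. Assuming four levels (the schema figure is not shown), four cohorts of 4 plus 2 more is 18 subjects, below 26 per part; six at one level is below 10.

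**The case against.** **The governing document is missing.** The SAP implements protocol Amendment 4, which was not supplied; the protocol supplied runs to Amendment 1. The SAP's Part 1 text also leaves out the minimum that the protocol states, so silence in the SAP is weak evidence about the plan as a whole. This stands, and it limits the point to SAP wording. The SAP does, however, restate completion rules for Parts 2 and 3, and a restated rule should be complete.

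**A DLT-free top dose may itself qualify as the MTCD**, which would bring in the six. That is possible, but rule 1 is written as a separate route for when no MTCD has been defined.

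**Safeguards exist.** SAP 7.1 says "the DLRT will make all dose level and dosing schedule decisions"; up to 10 subjects may be added at the top dose; and "a single grade 3 treatment related troponin elevation will result in dose de-escalation regardless of number of subjects treated at current dose". These reduce the practical risk. But the first two permit more subjects without requiring them, and the third covers one toxicity.

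**The minimum also penalises an acceptable dose.** This stands: at the target rate of 0.20 completion falls too, and with cohorts of 4 the loss is about 2 points at either rate, so the change barely separates a bad dose from a good one there.

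**The upper bounds overstate the uncertainty**, since they ignore lower levels and the 24 Part 1 subjects, and Table 1 already accepts 0/2 or 0/3 for going higher. Fair; they describe the top cohort and are not a decision criterion.

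**The missing MTD wording matters less.** SAP 2.1 gives Parts 2A and 2C safety and tolerability objectives without MTD estimation. Also fair.

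**Conclusion.** The gap in SAP 3.3 is real: followed literally, rule 1 completes escalation on an initial top-dose cohort of 2-4 or 3-4 subjects, with no evaluable minimum, unlike Part 1. It is a modest point, worth fixing because the fix is cheap and uses the sponsor's own number.

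The benefit lies mainly with cohorts of 2 (2A and 2C only) or 3. The sizes rest on two assumptions: the review team adds nobody voluntarily, and one DLT in six at the top dose still allows completion, which would have to come through rule 2 because rule 1 fails once any DLT occurs. The SAP defines the MTCD for that purpose but not a monotherapy MTD.

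Three stronger inferences are not supported:

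- A reader might infer that six subjects would cut the 0.33 figure to 9%, the chance of 0/6. Table 1 does not de-escalate at one in six, so the figures are 27%, 22% and 18%.
- A reader might infer that the DLT-free top dose passes automatically into expansion. The SAP does not say so, leaves dose decisions to the review team, and lists no expansion for Part 2C.
- A reader might infer that the trial has no such minimum at all. Amendment 4 may contain one.

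**What to change.** In SAP 3.3, add to rule 1: *with at least 6 evaluable subjects treated at that dose level*. Reword the sentence on the minimum so that it covers the MTD, the MTCD or the highest planned dose. A DLT among the added subjects is then handled by Table 1 and rule 2. Check Amendment 4 first; if it already sets a minimum, carry that wording into the SAP.

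The cost is 2-4 more evaluable subjects per part at the top dose (2-3 in Part 3), within the existing caps; about one more DLT window of at least 28 days; and the somewhat lower chance, shown above, of completing at a top dose whose true rate is on target.

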**Note:** Patients with measurable disease in both serum (SPEP) and urine (UPEP) at study entry are required to meet response criteria in both UPEP and SPEP in order to qualify for a MR or better. Conversely, it should be noted criteria for PD only needs to be met, and confirmed, in 1 parameter. For patients without measurable protein on UPEP at Baseline, UPEP will need to be repeated to confirm a response.

- a Patients with measurable disease in both serum (SPEP) and urine (UPEP) at study entry are required to meet response criteria in both UPEP and SPEP in order to qualify for a MR or better. Conversely, it should be noted that criteria for PD only needs to be met, and confirmed, in one parameter.
- b **All response categories (CR, sCR, VGPR, PR) require 2 consecutive assessments** made at any time before the institution of any new therapy, as well as no known evidence of progressive or new bone lesions if radiographic studies were performed. Radiographic studies are not required to satisfy these response requirements. Bone marrow, plasmacytoma, and skeletal survey assessments are not required to be confirmed by repeat testing. SD requires a duration of  $\geq 6$  weeks.
- c Presence/absence of clonal cells is based upon the  $\kappa/\lambda$  ratio. An abnormal  $\kappa/\lambda$  ratio by immunohistochemistry and/or immunofluorescence requires a minimum of 100 plasma cells for analysis. An abnormal ratio reflecting presence of an abnormal clone is  $\kappa/\lambda$  of  $> 4:1$  or  $< 1:2$ .
- d **Determination of PD while on study requires 2 consecutive assessments** made at any time before classification of PD and/or the institution of new therapy. Serum M-component increases of  $\geq 1$  g/dL from nadir are sufficient to define progression if nadir M-component is  $\geq 5$  g/dL.
- e Plasmacytomas: A definite increase in the size is defined as a  $\geq 50\%$  increase as measured serially by the sum of the products of the cross-diameters of the measurable lesion. A plasmacytoma is considered measurable if the longest diameter is at least 1 cm and the product of the cross diameters is at least 1 cm^2. Plasmacytomas of lesser size will be considered non-measurable.
- f The requirement for bi-directional measurements applies only to plasmacytomas.
- g The plasmacytoma specifications for PD are based on interpretation of the IMWG-URC and practical considerations for study execution.

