9.1 General Considerations

Descriptive statistics on continuous data will include means, medians, standard deviations and ranges, while categorical data will be summarized using frequency counts and percentages. Graphical summaries of the data may also be presented. When data are summarized by time, the values recorded against the scheduled time points listed in the protocol will be used. When assessing minimum/maximum increases or decreases over the study, all assessments, including unscheduled assessments will be used.

For each indication, efficacy and safety data will be summarized by dose level.

For the subjects who complete the DLT period and proceed to a higher dose level or crossover to a combinational therapy cohort for the following treatment cycle,

efficacy and safety data will be summarized per their initial assigned dose level.

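### The SAP's best-response rule states neither the confirmation that the protocol's myeloma criteria require nor a cut at new therapy or crossover, so read literally it can overstate ORR

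*SAP*

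**What the plan says.** **SAP Section 5, Best Overall Response.** "Best overall response for a subject is the best observed post-baseline disease response based on investigator assessment". A list of criteria follows, with "IMWG-URC for MM" and named criteria for AML, MDS and NHL.

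**SAP Section 5, Overall Response Rate.** A responder has PR or better by investigator assessment. The only time limit is the cutoff: "All subjects that do not meet the criteria for response (PR or better) by the analysis cutoff date will be considered as non-responders".

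**SAP Section 5, Duration of Response.** "It is defined as time from the first observation indicating a response to the subsequent date of disease progression or death, whichever is earlier". Time to response also ends at the first documented response.

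**Protocol Appendix E, footnote b.** "All response categories (CR, sCR, VGPR, PR) require 2 consecutive assessments", and these must be "made at any time before the institution of any new therapy". The footnote exempts bone marrow, plasmacytoma and skeletal survey assessments from repeat testing. Footnote d sets a matching rule for progression, which also needs two consecutive assessments.

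**SAP Section 9.1.** Once the DLT window is over, a subject may move up a dose or cross over to a combination cohort. The SAP then fixes where that subject is reported: "efficacy and safety data will be summarized per their initial assigned dose level".

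**SAP Section 10** declares no departure from the analyses in the protocol.

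**The concern.** There are two gaps.

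**Confirmation in myeloma.** Each Appendix E category is defined by thresholds that a single visit can meet; for PR, for example, a serum M-protein reduction of at least 50% with the matching urine condition. The two-assessment requirement sits in a footnote and has to be derived across visits. The SAP does not write that derivation down in its BOR, ORR, DOR or TTR definitions, or in its efficacy methods (Section 9.5). Nor does it point to Appendix E, which is marked there as modified for this protocol. Two competent programmers could therefore obtain different myeloma response rates from the same data.

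**The end of the response window.** Nothing in the BOR or ORR definition stops the search for a best response when a subject starts another treatment. Together with SAP 9.1, this affects subjects who cross over from monotherapy to a combination cohort, whatever their indication.

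ORR is the activity measure named in the protocol's clinical hypothesis (Section 2.4) and the first-listed secondary efficacy endpoint in the SAP. DOR and TTR use the same responders and the same start date.

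**Working it through.** **1. The plan's own figure.** SAP 3.2 gives n = 20 and ORR 20%, with a two-sided exact 95% CI of 6% to 44%. SAP 9.5 names the Clopper-Pearson method. For x responders of n, the lower limit is the 0.025 quantile of Beta(x, n − x + 1) and the upper limit is the 0.975 quantile of Beta(x + 1, n − x). With x = 4 and n = 20 this gives 5.73% to 43.66%, so the stated interval reproduces.

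**2. Direction for ORR.** Every subject with a response at two consecutive assessments before new therapy also has at least one observed response. The confirmed responders are thus a subset of the observed responders. Requiring confirmation, or closing the window earlier, can remove responders but cannot add any. Any error in ORR from the literal reading is upward or nil.

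**3. Size per subject.** One reclassified subject changes ORR by 1/20 = 5 points. SAP 3.2 plans up to 20 subjects in each expansion group, which for myeloma is Part 3C. Around the planning case:

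| Responders of 20 | ORR | Exact 95% CI |
|---|---|---|
| 2 | 10% | 1.2% to 31.7% |
| 3 | 15% | 3.2% to 37.9% |
| 4 | 20% | 5.7% to 43.7% |
| 5 | 25% | 8.7% to 49.1% |
| 6 | 30% | 11.9% to 54.3% |

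If four responders are observed and none, one or two of them are unconfirmed, the ORR under Appendix E is 20%, 15% or 10%. If two are added to four true responders, it rises to 30%. The counts of one and two are assumptions chosen to show the scale, since the documents give no rate of unconfirmed response.

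**4. DOR and TTR.** Take a subject who is a responder under both rules. The first observed response cannot be later than the first of a confirmed pair. The literal reading therefore makes that subject's TTR the same or shorter, and DOR the same or longer. Across the group the direction is not fixed, because the set of responders also changes.

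**5. Crossover, step by step.** A subject starts on monotherapy and has no response. The subject then moves to a combination cohort, and PR is first recorded there. That PR falls after baseline, so it becomes the BOR. It falls before the cutoff, so the subject is a responder. SAP 9.1 places the subject's efficacy data at the initial dose level. The PR is thus counted in the monotherapy ORR.

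**The case against.** **Confirmation may already come in by reference.** The SAP names IMWG-URC directly after the BOR sentence, and ORR counts only subjects who meet the response criteria. Appendix E is the protocol's version of IMWG-URC, and footnote b is part of it. The protocol also builds confirmation into assessment: repeat 24-hour UPEP for VGPR or CR (7.2.10.1), plasmacytoma evaluation to confirm PR or better (7.2.10), and marrow sampling to confirm CR (7.2.10.6). If investigators record only confirmed responses, the effect is zero. This stands as a possible reading. It does not remove the ambiguity, because the SAP speaks of observed responses and never says whether confirmation is applied by the investigator or in the derivation.

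A reader might infer more than the documents support:

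- **That the SAP prescribes the best single visit.** It never uses that word. What is shown is an omission, not a contradiction.
- **That ORR is inflated by a known amount.** A spurious-response model would need a per-visit error rate, and none is given.
- **That all indications conflict with their criteria.** The ELN (Appendix J) and Lugano (Appendix I) tables state no confirmation requirement for response, and the MDS criteria are not in the supplied documents. The confirmation point is limited to myeloma.
- **That responses after outside therapy are widely counted.** Protocol 6.10 excludes antitumor therapy during the study, and new systemic therapy ends AMG 397 (6.2.1.3). The safety follow-up visit lists no disease assessment (7.4.4). Long-term follow-up covers survival, progression and subsequent therapy only (7.4.5). Section 8.1 lets subjects off product continue assessments, but schedules none after new therapy. Crossover is the concrete route.

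ORR is also secondary and descriptive, with no hypothesis test (SAP 2.2). That limits the consequence but does not settle how ORR is to be derived.

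**Conclusion.** The point holds as a gap in the derivation. For myeloma, the SAP leaves it ambiguous whether a response must be confirmed. The literal reading can raise ORR and shift DOR and TTR, but need not. At n = 20 each misclassified subject is worth 5 points. How many there would be cannot be estimated from the documents, and the answer is none if recorded responses are already confirmed.

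The crossover gap is separate and does not depend on confirmation. As written, a response first seen on combination therapy counts in the monotherapy ORR. Its size depends on how many subjects cross over and then respond, which the documents also do not give.

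One limit applies throughout. The SAP implements protocol Amendment 4, whereas the supplied protocol runs to Amendment 1 and does not contain Parts 2 and 3 as the SAP describes them. The comparison assumes that the myeloma response appendix kept its two-assessment rules.

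**What to change.** In SAP Section 5:

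- **Myeloma.** Count sCR, CR, VGPR or PR only when confirmed at two consecutive assessments per Appendix E, keeping its exemption for marrow, plasmacytoma and skeletal survey. Date the response to the first of the pair.
- **All indications.** Use only assessments up to the earliest of progression, start of new anti-cancer therapy, or crossover to a combination cohort. For myeloma, progression here means progression confirmed per footnote d; cutting at an unconfirmed progression would breach the same appendix and could discard true responders.
- **Consistency.** Use the same responders for ORR, DOR and TTR, and list unconfirmed and post-crossover responses separately.

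Check the wording against the response appendices in Amendment 4 before adopting it.

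The cost is SAP text and programming. The supplied protocol already schedules repeated myeloma marker collections (seven in Table 6) and collects subsequent therapy in expansion; whether Amendment 4 does the same for Parts 2C and 3C needs confirming. The downside is that ORR may be slightly lower.
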